6.4.1.4 Exploratory Safety Analyses

Exploratory safety endpoints are:

- TIMI clinically significant bleeding,
- TIMI major bleeding,
- TIMI minor bleeding,
- BARC bleeding definition type 2, 3, 5,
- BARC bleeding definition type 3, 5
- BARC bleeding definition type 1, 2, 3, 5, and.
- BARC bleeding definition type 1.

For these endpoints the analyses follow the the estimations for the other bleeding. Descriptive tables of crude incidences of investigator-reported bleeding will be shown for all bleeding scales (ISTH, TIMI, BARC). A table will compare adjudicated and investigatorreported bleeding outcomes.

6.4.2 Subgroup analyses

For the primary endpoint and the endpoint all bleeding, subgroups analyses will be done for the following subgroups:

- Treated with NOAC at randomization (yes/no)
- Atrial fibrillation paroxysmal, persistent/permanent
- Weight (<60; 60-90; >90 kg)
- Age Group (< 65 years, 65 75 years, > 75 years)
- eGFR: <50; 50-80; >80 mL/min
- Risk factors for apixaban dosage (0-1, 2-3)
- Sex
- Race: White, Black, Asian, other
- Region: North America; Western Europe; Eastern Europe; Asia (Japan)
- Stroke or TIA prior to enrollment (yes/no)
- Treated with mild and moderate CYP3A4 inhibitors + inducers at randomization (yes/no)
- CHA2DS2VASc-Score (2&3 vs. > 3 for male participants, 3&4 vs. >4 for female participants)

For these subgroups descriptive tables of crude incidence will be presented. In treatment arms with 3 or more events exposure-adjusted incidence rates will be presented.

Comparison between treatment arms is only planned for the following subgroups:

- Treated with NOAC at randomization (yes/no)
- Stroke or TIA prior to enrollment (yes/no)
- Atrial fibrillation paroxysmal, persistent/permanent
- Risk factors for apixaban dosage (0-1, 2-3)

6.4.3 Analyses related to COVID-19

Analysis due to COVID-19 pandemic will be described in this section but might affect all sections of the analyses.

A description of the number of study participants whose assessments and follow up in the study was impacted by the COVID-19 pandemic will be shown. In addition, a listing of all study participants affected by the COVID-19 pandemic by unique subject number identifier and by investigational site, and a description of how the individual's participation was altered will be created.

For the primary safety estimand the intercurrent event "Treatment discontinuation due to COVID-19 related events" will be handled similar to any other premature discontinuation, i.e. all events from first intake of study drug up until 2 days after the last intake of study treatment will be counted.

Subgroup analyses for incidence tables will include the subgroup "Participants that are effected to any site closing due to COVID-19" will include all subjects that are randomized at sites that are closed due to COVID-19 before their individual end of treatment visit, resp. last study contact date, whatever is earlier. If there are more than one phase of closing in a site no distinction between the phases will be done.

Page: 23 of 25:

Demographics, Medical history as well of the tables showing the number of participants with an efficacy or safety event will be additionally shown for this subgroup.

Protocotol deviations due to COVID-19 will be shown in the protocol deviations section as a separate category.

COVID-19 disease itself will be counted as an adverse event and therefore listed in the repective adverse event tables

If the number of patients with a dignosed COVID-19 disease is sufficiently high (i.e. 10 participants or more), the following sensitivity analyses will be done for the efficacy and safety outcomes:

The primary estimand will handle the COVID-19 disease with an "while not having COVID-19 disease" approach and censor any patients data 14 days before the (first) start of a COVID-19 disease.

In addition the number of subjects with an event occurring after COVID-19 disease will be shown for efficacy and safety events.

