- participant on a NOAC in case of at least one bleeding risk feature (history of a prior bleed within the last 12 months requiring medical attention and / or moderate renal dysfunction with eGFR 30-50 ml/min and / or current clinically indicated antiplatelet therapy with acetylsalicylic acid [ASA] ≤ 100 mg).

Stratification will be based on whether participants received a NOAC before study start or were not treated with any oral anticoagulant.

The planned study duration will be 14-16 weeks, consisting of:

- Screening period (visit 1 until visit 2): 2 weeks (participants will be screened and have to be randomized within 2 weeks of screening. If all information is available, a participant can be randomized on the day of screening (visits 1 and 2 are combined).
- Treatment period (from visit 2 through visit 6 [EOT] or visit 6a [ET]): 12 weeks
- Safety follow-up (visit 7 [SFU]): 14 days (+ 7 days) after EOT or ET.

Study visits will take place as visits at the study sites and telephone calls. Visits at the study sites take place at screening and randomization (visit 1 and visit 2), at week 4 (visit 4) and week 12 (i.e. EOT, visit 6).

[figure not shown]
Telephone calls will take place at week 2 (visit 3), week 8 (visit 5), as well as 2 weeks after the EOT visit for participants who will take study intervention until the planned EOT (i.e. SFU, visit 7).

For participants who prematurely discontinue from study intervention, an early termination (ET) visit (visit 6a) will take place as soon as possible as visit at the study sites. Telephone calls take place 14 days after the ET visit (i.e. SFU, visit 7).

The study design is presented in Figure 3-1: Study design overview.

Page: 7 of 25:

Figure 3-1: Study design overview

Duration of Treatment: 12 weeks

Note: Participants receiving BAY 2433334 will also receive the apixaban matching placebo. Participants receiving apixaban will also receive the BAY 2433334 matching placebo. During the safety follow-up, further therapy (e.g. NOAC) is at discretion of the investigator.

4. General Statistical Considerations

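### The COVID-19 site-closing subgroup has a latest date for the closure but no earliest date, so read literally it also takes in participants randomised after their site had reopened

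*SAP*

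**What the plan says.** SAP section 6.4.3 names a subgroup, "Participants that are effected to any site closing due to COVID-19", for the incidence tables. The rule is that it "will include all subjects that are randomized at sites that are closed due to COVID-19 before their individual end of treatment visit", with an alternative limit: "resp. last study contact date, whatever is earlier". On repeated closures it adds: "If there are more than one phase of closing in a site no distinction between the phases will be done".

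The use is descriptive. Demographics and medical history are repeated, and the "tables showing the number of participants with an efficacy or safety event will be additionally shown for this subgroup".

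The same section also plans a count of participants whose assessments or follow-up were affected by the pandemic, and a listing by participant and site for which "a description of how the individual's participation was altered will be created". COVID-19 protocol deviations form their own category.

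No other section of the SAP gives an earliest date for the closure or mentions a site reopening.

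**The concern.** The label describes people whose participation a closure touched. The rule tests only whether the site's closure came before the participant's end of treatment or last contact. A closure that was over before the participant was randomised passes that test.

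After randomisation, the scheduled on-site visits are at weeks 4 and 12 (SAP section 3). A closure within that window can disturb them. A closure that ended before randomisation cannot disturb them in the same way. If both kinds of participant are in one table, any difference among those whose follow-up was really interrupted is averaged with people whose visits ran as planned. What is at stake is how far the repeated descriptive tables can be interpreted, not any inferential result.

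**Working it through.** The SAP states no figure on this point, so there is nothing to reproduce. The check is one of logic, followed by an illustration of scale.

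**Step 1: the rule against the label.** For one participant and one closure phase, let R0 be the randomisation date, E the earlier of end-of-treatment visit and last study contact, C0 the closure start and C1 the closure end.

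- Rule as written: C0 before E.
- Rule that matches the label: C0 before E, and C1 on or after R0.

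| Closure relative to the participant | As written | Overlap rule |
|---|---|---|
| Starts after E | out | out |
| Starts between R0 and E | in | in |
| Starts before R0, still in force at R0 | in | in |
| Starts and ends before R0 | **in** | **out** |

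The two rules differ only in the last row, which is the participant randomised after reopening.

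**Step 2: scale at one site.** Inputs:

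- Treatment window, from SAP section 3: "Treatment period (from visit 2 through visit 6 [EOT] or visit 6a [ET]): 12 weeks".
- Assumed, because the SAP gives no dates: constant weekly accrual, a single closure, no randomisation while closed, every participant completing 12 weeks, P weeks of recruitment before closure and R weeks after reopening.

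Participants randomised more than 12 weeks before the closure have finished treatment and are excluded under either rule. In weeks of accrual:

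- Truly overlapping = min(P, 12)
- Included without overlap = R
- Share of members without overlap = R / (min(P, 12) + R)

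| Weeks recruiting after reopening (R) | P of 12 or more | P = 4 |
|---|---|---|
| 0 | 0/12 = 0% | 0/4 = 0% |
| 4 | 4/16 = 25% | 4/8 = 50% |
| 12 | 12/24 = 50% | 12/16 = 75% |
| 26 | 26/38 = 68% | 26/30 = 87% |
| 52 | 52/64 = 81% | 52/56 = 93% |

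These are shares at a single site that closed and reopened. The share across the trial depends on how many sites did so and on how much they recruited afterwards, neither of which the SAP gives. A site that never resumed recruitment contributes 0%.

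**The case against.** The strongest reply is that the sentence can be read in sequence: the participant is randomised, and the site then closes before that participant's end of treatment. On that reading randomisation is the implied start, and the label supports it. This is a possible reading, so it cannot be asserted that the tables will in fact be filled with undisturbed participants. It does not remove the point, because the sentence does not say this and two programmers could derive different subgroups from it. The sequential reading also has its own gap: it would leave out anyone randomised while a closure was already in force.

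A reader might infer from the sentence on closing phases that one early closure is meant to mark everyone later randomised at the site. The SAP does not support that. The sentence may mean only that participants affected by a first or a later closure are pooled and not tabulated separately. It neither causes nor cures the missing start limit.

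A reader might also infer that the tables would give false reassurance about bleeding or its ascertainment. Section 6.4.3 states no such purpose, and no test, threshold or conclusion depends on this subgroup. Section 6.4.2 names the only subgroups with planned comparisons between arms, and this is not among them. Disruption is also visible elsewhere: in the participant-level listing, in the COVID-19 deviation category, and in the visit adherence tables of section 6.1.1, which separate in-person, telephone and third-party contact. All of this stands and lowers the weight of the point. It does not correct the repeated event tables, which are built from the rule as written.

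**Conclusion.** The point holds as a minor defect in a stated rule. Section 6.4.3 limits the closure from above only, and taken literally it admits participants whose time in the study no closure overlapped, contrary to the subgroup's own label.

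The size cannot be determined from the SAP. With constant accrual and at least 12 weeks of recruitment before closure, the share wrongly included at an affected site runs from 0% to 81% as recruitment after reopening runs from 0 to 52 weeks. With less recruitment before the closure, the share is higher for the same R. It would be wrong to conclude that most of the subgroup is misclassified, since the true share may be zero.

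The primary safety estimand and its analysis, the analysis sets and the planned between-arm subgroup comparisons are unaffected.

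**What to change.** Reword the membership rule in section 6.4.3 so that a participant is included if at least one day of any COVID-19 closure phase at their site falls between randomisation and the earlier of end-of-treatment visit and last study contact. State that each phase is checked against that interval and that participants qualifying through any phase are pooled into one subgroup. This keeps the single pooled subgroup while making clear that pooling does not replace the overlap check.

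The cost is small: one sentence of SAP text, and closure end dates as well as start dates for each site. No other analysis changes.

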6.4.4 Vital Signs

Vital signs (systolic and diastolic blood pressure, heart rate) obtained at Visit 1 (Screening), Visit 2 (Randomization (if not on the same day as Visit 1)), Visit 4 as well as during Final visit (Visit 6) and Early termination visit (Visit 6a) will be displayed by means of descriptive statistics and change from baseline.

6.4.5 Laboratory parameter

Only centrally analyzed blood samples will be considered for analysis.

Central laboratory parameters (e.g. AST, ALT, eGFR) obtained at Visit 1 (Screening), Visit 2 (Randomization (if not on the same day as Visit 1)), Visit 4 as well as during Final visit (Visit 6) and Early termination visit (Visit 6a) will be displayed by means of descriptive statistics and change from baseline.

Number of participants with treatment emergent high abnormalities will be shown overall and by visit for the following laboratory parameter:

- AST or ALT > 3xULN
- AST and/or ALT >3xULN and bilirubin > 2xULN
- AST or ALT >5xULN
- AST or ALT >8x ULN.

6.4.6 Biomarker

Exploratory biomarker analyses, that might be performed optionally and/or only in a subset of participants are:

- NT-proBNP
- hsCRP
- Thrombin-activatable fibrinolysis inhibitor (TAFI)
- C1 inhibitor activity
- TAT, and
- F1.2

The analyses will be performed at Visit 1 before the first dose and at the final Visit or Early Termination visit prior to the dose of open-label anticoagulant.

The biomarkers will be by means of descriptive statistics and change from baseline.

6.4.7 Electrocardiograms

A single 12-lead ECG will be performed at Visit 1 (Screening), Visit 2 (Randomization (if not on the same day as Visit 1)) as well as during Final visit (Visit 6) and Early termination visit (Visit 6a). QRS, QT and QTc intervals will be displayed by means of descriptive statistics and change from baseline.

The number of participants with abnormal electrocardiograms findings will be displayed by visit.

6.4.8 Adverse events

The investigator has to record on the respective CRF pages all adverse events occurring in the period from start of intervention (first day of study intervention) until the safety follow-up visit. The original terms used by investigators to report AEs via the CRFs will be coded using the Medical Dictionary for Regulatory Activities (MedDRA).

For each AE, the number and percentage of participants who experienced at least 1 occurrence of the given event will be tabulated according to the affected primary system organ class (SOC) and preferred term (PT) by randomized treatment arm. A total column will be included in all safety summaries.

Frequency tables, showing an overall summary of number of participants with AEs, study drug related AEs, SAEs and AESIs will be given, and will include the following information:

- maximum intensity for any AE,
- AE related deaths,
- AE resulting in permanent discontinuation of study drug,
- treatment emergent AE.

AEs will be considered treatment-emergent if they begin after the first administration of study drug and they do not start after more than 2 days after the last administration. Determination of whether or not an event is treatment-emergent will be derived after the missing or incomplete AE start date is imputed. Imputation rules for missing and incomplete AE start data are described in section 4.3.

The severity or intensity of an (S)AE should be graded by the investigator with the following guidance:

- Mild: An event that is easily tolerated by the participant, causing minimal discomfort and not interfering with everyday activities.
- Moderate: An event that causes sufficient discomfort and interferes with normal everyday activities.
- Severe: An event that prevents normal everyday activities. An AE that is assessed as severe should not be confused with an SAE. Severe is a category utilized for rating the intensity of an event; and both AEs and SAEs can be assessed as severe.

An event is defined as 'serious' when it meets at least 1 of the predefined criteria as described in the definition of an SAE, not when it is rated as severe.

6.4.9 Pregnancies

Any reported pregnancy occurring in female participants will be displayed. In addition, any reported pregnancy occurring in female partners of male participants after start of study intervention up until 4 days of the last intake of study drug will be displayed.

7. Document history and changes in the planned statistical analysis

- SAP Version 1.0 completed 10 DEC 2019
- SAP Version 2.0: Changes in categorization of age added SAS code and statement on multiplicity adjustment, clarification of exploratory efficacy variable; add section for COVID-19 related (sensitivity) analyses; update Pharmacokinetics analysis part; changes in subgroups; add TIMI minimal bleeding definition, completed on 14 OCT 2021

8. References

- Aalen, Borgan, and Gjessing. Survival and Event History Analysis. New York: Springer, 2008.
- Allignol, Beyersmann, and Schmoor. "Statistical issues in the analysis of adverse events in time-to-event-data." *Pharmaceutical Statistics*, no. 15 (2016): 297-305.
- Gray. "A class of k-sample tests for comparing the cumulative incidence risk of a competing risk." *The Annals of Statistics* 16, no. 3 (1988): 1141-1154.

Nelson. Applied Life Data Analysis. New York: Wiley, 1982.

Unkel, et al. "On estimands and the analysis of adverse events in the presence of varying follow-up times within the benefit assessment of therapies." *Pharmaceutical Statistics*, no. 18 (2019): 166-183.
